3.4 Pharmacokinetic and Immunogenicity Variables

3.4.1 PK parameters

PK parameters (including C_{max} , C_{min} , AUC, and others) is primary endpoint of dose-finding phase and will be used to facilitate the determination of the RP2D.

Individual durvalumab and tremelimumab concentrations in serum (C_{\max} and C_{\min}), time to C_{\max} and AUC will be used to describe the PK of durvalumab and tremelimumab.

Pharmacokinetic non-compartmental analysis

The actual sampling times will be used in the PK calculations. PK parameters will be determined using standard non-compartmental methods.

3.4.2 ADAs

The presence of ADA will be assessed in serum samples for patients with solid tumors. Samples will be measured for the presence of ADAs and ADA-neutralizing antibodies for both durvalumab and tremelimumab using validated assays.

3.5 Biomarker Variables

The following exploratory biomarkers will be collected

CCI

CCI

4 ANALYSIS METHODS

4.1 General principles

The primary analysis cut off will be defined at approximately 6 months after enrollment of the last patient. At this point, data analysis will be performed, and the CSR will be written. After this, patients still in the study will continue to be followed and a CSR addendum will be issued for OS and safety data collection.

For PK and other biomarkers, the sample bioanalysis will be performed by AstraZeneca or a contracted laboratory. PK parameters will be derived by Labcorp. The merging of PK concentration data with actual elapsed time from dose for PK sampling times will be performed by IQVIA Programming. The PK summaries and data listings will be the responsibility of IQVIA Biostatistics.

Statistical summaries and analyses of non-PK data will be performed by IQVIA under the direction of the Biostatistics Group, AstraZeneca using SAS® version 9.4 or higher and, where appropriate, additional validated software.

There is no formal statistical testing for the dose-finding phase of the study.

The dose-expansion phase of the study will formally test the following hypothesis:

- H_0 : ORR \leq 10%
- H_1 : ORR $>$ 10%.

The test will be done at the 1-sided 5% level and it will be performed for the SARCOMA cohort.

No formal statistical testing will be performed for the STO cohort.

For the dose-finding phase, and dose-expansion phase where relevant, dose levels will be labelled in summary tables as:

- durvalumab xx mg/kg + tremelimumab xx mg/kg

with xx depending on the dose levels used.

For the dose-expansion phase, cohorts will be labelled in summary tables as:

- SARCOMA
- STO

Total columns will be included for the dose-finding and dose-expansion phases separately for outputs where a total column is required.

Visits will be present as cycle and day (e.g. Cycle 1 Day 1). Study day will be calculated as follows:

Days prior to first dose: Study day = date – first dose date

Days on or after first dose: Study day = date – first dose date + 1

First dose refers to either durvalumab or tremelimumab, whichever was administered first. Dates of progression will not be imputed.

The end of study is defined as the last expected visit/contact of the last patient undergoing the study. A patient is considered to have completed the study when he/she has completed his/her last scheduled visit shown in the schedule of activities (CSP section 1.1).

Categorical data will be summarized by the number and percentage of patients in each category. Continuous data will be summarized using descriptive statistics, including n, arithmetic mean, STD, median, minimum, and maximum values. Additionally, geometric means and coefficient of variation (CV)% will be reported for PK variables (concentrations and all PK parameters). The geometric mean is calculated as the exponential of the arithmetic mean calculated from data on a log scale. All data will be listed.

4.1.1 Rounding and precision

- For continuous data, the mean and median will be rounded to 1 additional decimal place compared to the original data. The standard deviation (STD) will be rounded to 2 additional decimal places compared to the original data. Minimum and maximum will be displayed with the same accuracy as the original data.
- For categorical data, percentages will be rounded to 1 decimal place.

If further guidance is needed the methods described in Section 5.2 of ‘Statistical guidelines for Clinical Pharmacology Alliance studies’ will be applied.

4.1.2 Baseline measurements and change from baseline

Baseline will be the last non-missing value obtained prior to the first dose/administration of study treatment (durvalumab or tremelimumab) and any information taken after first dose/administration of study treatment is regarded as post baseline information in the relevant phase. If two visits are equally eligible to assess patient status at baseline (e.g., screening and baseline assessments both on the same date prior to first dose/administration with no washout or other intervention in the screening period) and time of assessment is not available, the average should be taken as the baseline value. For non-numeric laboratory tests (i.e. some of the urinalysis parameters) where taking an average is not possible then the best value would be taken as baseline as this is the most conservative. In the scenario where there are two assessments on the same day one with time recorded and the other without time recorded, the one with time recorded would be selected as baseline. If no value exists before the first dose/administration, then the baseline value will be treated as missing. For questionnaires where multiple records are eligible to be used as the baseline value and time of assessment is not available, the best scenario will be flagged as this is the most conservative.

Absolute change from baseline outcome variables is computed as
(post baseline value – baseline value).

Percent change from baseline is computed as

$$((\text{post baseline value} - \text{baseline value}) / \text{baseline value}) \times 100\%$$

If either the post-baseline value or the baseline value is missing, then the absolute or percent change from baseline value will also be set to missing.

4.1.3 Time Windows

Safety assessments

Time windows will need defining for any presentations that summarize values by visit. The following conventions apply:

- The time windows should be exhaustive so that data recorded at any time point has the potential to be summarized. Inclusion within the time window should be based on the actual date and not the intended date of the visit.
- All unscheduled visit data should have the potential to be included in the summaries.
- The window for the visits following baseline will be constructed in such a way that the upper limit of the interval falls halfway between the two visits (the lower limit of the first post-baseline visit will be Day 2). If an even number of days exists between two consecutive visits, then the upper limit will be taken as the midpoint value minus 1 day. For example, the visit windows for vital signs data in the dose-expansion phase for patients' treatment with durvalumab in combination with tremelimumab are:
 - Cycle 1 Day 8 visit window day 2-11
 - Cycle 1 Day 15 visit window day 12 - 21
 - Cycle 2 Day 1 visit window day 22 - 35
 - Cycle 2 Day 15 visit window day 36 - 49
 - Cycle 3 Day 1 visit window day 50 – 63
 - etc
- The upper limit for the last record on treatment will consider end of treatment date and not date of disease progression.
- For summaries showing the maximum or minimum values, the maximum/minimum value recorded on treatment will be used (regardless of where it falls in an interval).
- Listings should display all values contributing to a time point for a patient.
- For visit based summaries:
 - If there is more than one value per patient within a time window then the closest value to the scheduled visit date should be used, or the earlier in the event the values are equidistant from the nominal visit date. The listings should highlight the value for that patient that went into the summary table, wherever feasible. Note: in summaries of extreme values all on-treatment values collected are used including those collected at unscheduled visits.
 - To prevent very large tables or plots being produced that contain many cells with meaningless data for outputs in the dose expansion phase, for each treatment group visit data should only be summarized if the number of observations is greater than the minimum of 5 of patients dosed.

- For summaries at a patient level, all values should be included, regardless of whether they appear in a corresponding visit-based summary, when deriving a patient level statistic such as a maximum.

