- r CCI [REDACTED]
- s See Section 6.1.4 and Section 8.1 for additional details. Imaging modalities appropriate for the tumor type under consideration should be performed and the corresponding objective criteria used to monitor efficacy: solid tumors (RECIST 1.1 [Appendix E], and INRC for neuroblastoma [Appendix F]). Confirmatory scans will be required.
- t A tremelimumab sample is required for patients at the EoT visit who only received a single dose (cycle) of tremelimumab in combination with durvalumab. Preferably, this sample should be collected approximately 30 days after the final tremelimumab infusion, but can be collected at any time after the final (day 15) tremelimumab PK sample.

ADA Anti-drug antibody; AE Adverse event; C Cycle; CR Complete response; CSF Cerebrospinal fluid; D Day; Durva Durvalumab; ECG Electrocardiogram; FFPE Formalin-fixed paraffin-embedded; HIV Human immunodeficiency virus; ICF Informed consent form; IM Intramuscular; INRC International Neuroblastoma Response Criteria; IP Investigational product; LFT Liver function test; LP Lumbar puncture; mRNA Messenger ribonucleic acid; NA Not applicable; CCI [REDACTED] PK Pharmacokinetics; PR Partial response; qXw Every X weeks; RECIST Response Evaluation Criteria In Solid Tumors; SAE Serious adverse event; CCI [REDACTED] Treme Tremelimumab; T3 Triiodothyronine; T4 Thyroxine; TSH Thyroid-stimulating hormone; W Week.

Table 2 Schedule of activities for durvalumab ± tremelimumab dose-expansion phase

	Screening	Cycle 1 (28 days)			Cycle 2 (28 days)		Cycle 3 to progression (each cycle is 28 days)	End of Treatment visit	For details, see Section
Day of cycle	-28 to -1	1	8	15	1	15	1		
Visit window^a			±3 days	±3 days	±4 days	±3 days	±4 days		
Informed consent									
Informed consent/assent: study procedures ^b	X								5.1
Study procedures									
Physical exam (full)	X								8.2.1
Targeted physical exam		X	X	X	X	X	X	X	8.2.1
Vital signs (including peripheral oxygen saturation)	X	X	X	X	X	X	X	X	8.2.3
Weight		X			X		X		8.2.1
Height		X			X		X		8.2.1
Tanner staging		X	To be measured at visits where tumor efficacy assessments are made (see Section 8.1), until progression						8.2.4
ECG ^c (single)	X	As clinically indicated							8.2.5
Concomitant medications (including vaccines)	X	X	X	X	X	X	X	X	6.4
Demography, including baseline characteristics and tobacco use ^d	X								5.1
Eligibility criteria	X								5.1, 5.2
Laboratory assessments									
Clinical chemistry ^e	X	X ^f		X	X	X	X	X	Table 19

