1.2 Study design

This is an open-label, non-randomized, international, multicenter study investigating durvalumab in combination with tremelimumab (q4w for 4 cycles only) followed by durvalumab monotherapy (q4w) in pediatric patients from birth to <18 years of age with relapsed or refractory malignant solid tumors. Each treatment cycle is 28 days.

The study will be conducted in 2 sequential phases; a dose-finding phase (Phase I) followed by a disease specific dose-expansion phase (Phase II). The purpose of this study is to identify the recommended Phase II dose (RP2D) that will be taken forward to determine preliminary antitumor activity of durvalumab in combination with tremelimumab in solid malignant tumors, using disease specific response criteria.

Dose-finding phase

The dose-finding phase of the study will be conducted using a 3 + 3 design to determine whether durvalumab and tremelimumab can be administered safely in children and if adult exposures can be achieved. Pediatric patients with relapsed or refractory solid malignant tumors including osteosarcoma and Ewing sarcoma (SARC-1), rhabdomyosarcoma, non-rhabdomyosarcoma, and other sarcomas (SARC-2), neuroblastoma (NB), and other solid tumors (STO), will be enrolled in 2 arms based on patient weight:

[figure not shown]
- Arm A: patients weighing ≥ 35 kg
- Arm B: patients weighing < 35 kg

Three dose levels may be explored in each of the arms as outlined in [Figure 1](#). Dose level 1 will be 100% of the recommended adult dose of both durvalumab and tremelimumab administered as weight-adjusted doses. The doses and schedules are as follows:

- 1 Cycle 1 (durvalumab monotherapy): durvalumab 20 mg/kg
- 2 Cycles 2 to 5 (durvalumab in combination with tremelimumab): durvalumab 20 mg/kg and tremelimumab 1 mg/kg [4 cycles administered every 28 days]
- 3 From Cycle 6 onwards, treatment will continue until a discontinuation criterion is met, with durvalumab monotherapy administered at 20 mg/kg q4w.

At least one day between first patient and subsequent patients dosed at each dose-level is required.

Figure 1 Dose levels – Dose-finding phase

This figure shows the maximum doses for durvalumab at DLs 2 and 3 (40 mg/kg) and tremelimumab at DL 3 (2 mg/kg). Lower doses may be tested, depending on the obtained PK modeling data.

DL Dose level; NB Neuroblastoma; SARC-1 Osteosarcoma and Ewing sarcoma; SARC-2 Rhabdomyosarcoma, non-rhabdomyosarcoma, and other sarcomas; STO Solid tumor other.

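### SAP 4.1.3: the worked example ends the Cycle 3 Day 1 vital-signs window at day 63, but the SAP's own midpoint rule gives day 70

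*SAP*

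**What the plan says.** SAP 4.1.3 (Time Windows, safety assessments) builds the windows so that "the upper limit of the interval falls halfway between the two visits (the lower limit of the first post-baseline visit will be Day 2"). It adds: "If an even number of days exists between two consecutive visits, then the upper limit will be taken as the midpoint value minus 1 day". It also requires that no day be left out: "The time windows should be exhaustive so that data recorded at any time point has the potential to be summarized". Assignment uses the actual date, and unscheduled values are eligible.

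The section then gives a numerical example, introduced as follows: "the visit windows for vital signs data in the dose-expansion phase for patients' treatment with durvalumab in combination with tremelimumab are". Five windows are listed: Cycle 1 Day 8 (2–11), Cycle 1 Day 15 (12–21), Cycle 2 Day 1 (22–35), Cycle 2 Day 15 (36–49), and finally "Cycle 3 Day 1 visit window day 50 – 63". The list closes with 'etc'.

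On timing, SAP 1.2 states: "Each treatment cycle is 28 days". Protocol Table 2, the dose-expansion schedule in section 1.1, has a single Day 1 column headed "Cycle 3 to progression (each cycle is 28 days"), and vital signs are marked in it. There is no Cycle 3 Day 15 column.

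**The concern.** The first three 14-day steps between visits end at Cycle 3 Day 1. After that the spacing doubles to 28 days, so the window after Cycle 3 Day 1 should widen. The printed window does not: it ends 6 days after the visit, just as the Cycle 2 Day 1 and Cycle 2 Day 15 windows do.

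This list is the only place where the SAP states by-visit windows as numbers. Two programmers could therefore produce different tables from the same section, one by applying the rule and the other by copying the list. The same conventions govern every by-visit safety presentation. Besides vital signs (SAP 4.2.3.4), that includes continuous laboratory data (SAP 4.2.3.3), for which Table 2 also schedules chemistry and hematology on Day 1 only from Cycle 3.

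**Working it through.** **Inputs.** Cycle length is 28 days (SAP 1.2), so study day = 28 × (cycle − 1) + day of cycle. The scheduled vital-signs visits after first dose come from protocol Table 2: days 8, 15, 29, 43, 57, 85, 113 and so on.

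**Rule.** Upper limit = midpoint of two consecutive visit days, less 1 if the gap is even. For an odd gap the midpoint is rounded down to a whole day. Each lower limit is the previous upper limit plus 1, and the first is day 2.

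| Visit | Day | Next visit | Gap | Midpoint | Upper limit by rule | Upper limit in SAP |
|---|---|---|---|---|---|---|
| Cycle 1 Day 8 | 8 | 15 | 7 | 11.5 | 11 | 11 |
| Cycle 1 Day 15 | 15 | 29 | 14 | 22 | 21 | 21 |
| Cycle 2 Day 1 | 29 | 43 | 14 | 36 | 35 | 35 |
| Cycle 2 Day 15 | 43 | 57 | 14 | 50 | 49 | 49 |
| Cycle 3 Day 1 | 57 | 85 | 28 | 71 | **70** | **63** |

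The rule reproduces the first four limits and fails only on the fifth. The next window under the rule is Cycle 4 Day 1, from day 71 to (85 + 113)/2 − 1 = 98.

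**Could another reading give 63?**
- If 'even' means the number of days strictly between visits, the limits become 10.5, 22, 36, 50 and 71. None agrees with the SAP.
- The dose-finding schedule also has only Day 1 visits from Cycle 3, so it too gives 50–70.
- An extra visit at Cycle 3 Day 15 (day 71) gives (57 + 71)/2 − 1 = 63. This is the only one of the three that returns the printed figure, and Table 2 has no such visit. Protocol 8.2.6 mentions that day only as a recommended contact.

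**Size of the discrepancy.** The rule's window has 70 − 50 + 1 = 21 days and the printed one has 63 − 50 + 1 = 14. The difference is the 7 days from 64 to 70. These are 7 to 13 days after Cycle 3 Day 1 and 21 to 15 days before Cycle 4 Day 1, so every one is nearer Cycle 3.

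**Which values can fall there.** Cycle 3 and Cycle 4 Day 1 visits carry a ±4-day allowance, that is days 53–61 and 81–89. Neither range meets days 64–70. A Cycle 3 Day 1 visit that is 7 to 13 days late does fall there, and protocol 1.1 permits delays of up to 14 days for adverse events. Unscheduled assessments can fall there too.

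**Illustration.** Suppose Cycle 3 Day 1 takes place on day 66 and Cycle 4 Day 1 on day 66 + 28 = 94, with no other values from day 50 onward. Under the rule, day 66 enters Cycle 3 Day 1 (50–70) and day 94 enters Cycle 4 Day 1 (71–98). Under the printed list:
- If Cycle 4 Day 1 starts at day 71, the day 66 value has no window.
- If Cycle 4 Day 1 starts at day 64, both values compete for it. SAP 4.1.3 keeps the one closer to day 85, which is day 94 (9 days away against 19).
- Either way, the patient drops out of the Cycle 3 Day 1 column.
- If the patient has no later value and Cycle 4 starts at day 64, the day 66 value is shown as Cycle 4 Day 1.

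**The case against.** The strongest defence is that the list is only an example. The binding text is the rule and the exhaustiveness requirement; a programmer who follows those obtains 50–70 and nothing is misplaced. That is right, and it is why the harm is conditional on the list being coded literally. It does not make day 63 correct, because an example that contradicts the rule it illustrates invites exactly that coding.

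The defence also limits the reach, and those limits stand. Maximum and minimum summaries use all on-treatment values wherever they fall, patient-level statistics include every value, and listings show all data. SAP 4.2.3 describes the safety summaries as descriptive only. Objective response, the primary endpoint of this phase, does not use these windows.

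Three stronger readings are tempting, and the documents do not support them:
- **That a week of safety values is lost or misassigned.** At most a value drops out of, or changes column in, a by-visit table, and only under literal coding.
- **That a third of the Cycle 3 data is affected, since 7 of 21 days are missing.** That counts calendar days; on-schedule visits never fall on those days. Where a patient has a closer value in the window, the closest-value rule selects that one anyway.
- **That the same gap recurs in every later cycle.** No later window is printed. 'etc' may mean a continued 14-day pattern, but the stated rule gives 71–98 for Cycle 4 Day 1.

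**Conclusion.** The printed upper limit of day 63 is wrong by the SAP's own rule; it should be day 70. The error is 7 days at one boundary, in a worked example for vital signs in dose-expansion. The arithmetic rests on the 28-day cycle and on Table 2 having no visit between Cycle 3 Day 1 and Cycle 4 Day 1.

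The practical effect is minor. It needs the example to be coded as printed, and a delayed or unscheduled value on days 64 to 70 from a patient with no closer value for that visit. It then reaches only by-visit descriptive safety summaries. This takes the ±4-day allowance around nominal study days 57 and 85; a visit that is late because an earlier cycle slipped counts here as delayed. The documents do not show how many such values there will be, so no proportion can be put on it. Nothing here bears on the safety conclusions drawn from extremes, or on any efficacy result.

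**What to change.** In SAP 4.1.3, change the Cycle 3 Day 1 window to day 50–70, and add a line for Cycle 4 Day 1 as day 71–98 before 'etc'. The added line shows the 28-day pattern that later cycles follow, so the continuation is no longer open to interpretation.

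The cost is two lines of text. Nothing changes in data collection, endpoints or analysis methods. If the by-visit programs already exist, check that they use the midpoint rule for Cycle 3 Day 1 and later visits, in laboratory as well as vital-signs tables.

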4.2 Analysis methods

The two phases of the study will be summarized and analyzed separately. For the dose-finding phase, summaries will be presented by dose level. For the dose-expansion phase, summaries and analyses will be presented by cohort (see section 4.1).

For the dose-finding phase, the arms based on patient weight (Arm A: patients ≥ 35 kg and Arm B: patients < 35 kg) will be summarized separately, along with an overall summary by dose level.

4.2.1 Multiplicity

Not applicable for this study.

4.2.2 Efficacy analysis

The following table (Table 9) presents the analyses planned for the efficacy endpoints. All tumor-related endpoints will be analyzed using Investigator RECIST 1.1 assessments. The efficacy analyses will be produced for the dose-expansion patients only.

Table 9 Pre-planned statistical analysis to be conducted

Endpoint analyzed	Notes
ORR	Exact 90% 2-sided CI (Mid-P)
DoR	Median estimated from KM curve
DCR	Exact 90% 2-sided CI (Mid-P)
BoR	n (%) of patients in each response category
PFS	Median estimated from KM curve
OS	Median estimated from KM curve
APF12	90% 2-sided CI estimated from KM curve
APF18	90% 2-sided CI estimated from KM curve
OS12	90% 2-sided CI estimated from KM curve
OS24	90% 2-sided CI estimated from KM curve

CI Confidence interval; KM Kaplan-Meier.

4.2.2.1 Objective response rate (ORR)

The ORR will be based on the programmatically derived (RECIST 1.1) outcome. The point estimate and 90% confidence interval (CI) (2-sided) of the ORR will be presented for each if the three analysis cohorts. If the cohort is expanded after the initial DRC review, the CI will be calculated using an exact Mid-P method (Porcher and Desseaux 2012). If the cohort is not expanded an exact CI will be presented.

90% Mid-p confidence limits are the values that have a one-sided Mid-p value of 0.05. (A Mid-p value for a one-sided test is obtained by including in the tail only one-half of the probability of the observed sample).

The exact Mid-p confidence limits θ_L (lower limit) and θ_U (upper limit) are those values which satisfy the equations:

$$\sum_{i=0}^n p_i(\theta_L) - \frac{1}{2}p_n(\theta_L) = 0.95$$

$$\sum_{i=0}^n p_i(\theta_U) - \frac{1}{2}p_n(\theta_U) = 0.05$$

This analysis will be performed on the evaluable for response analysis set.

Summaries will be produced that present the number and percentage of patients with a confirmed tumor response (CR/PR).

Sensitivity analyses will be performed for tumor response (CR/PR) on FAS and "unconfirmed CR/PR" on the evaluable for response analysis set.

